6.3 Study Dates

End of Study Date

Date of the End of Study (EOS) safety follow-up phone call (for subjects who complete the study) or Early Termination (ET) visit (for subjects who withdraw from the study prematurely).

First Dose Date

The date of the first dose of IP.

Last Dose Date

The date of the last dose of IP.

Randomization Date

The date when a randomization number is assigned through the Interactive Voice/Web Response System (IVRS/IWRS).

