6.4 Study Time Intervals

Double-blind Treatment Period

The period of time beginning when a subject receives their first dose of IP through the first dose of rescue treatment, or end of study if they are never rescued. In case where a

subject is randomized but never dosed, the double blind period will start on the randomization date.

Rescue Therapy Period

The period of time between the first dose of open-label rescue therapy at or after week 24 through end of study.

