lateral epicondyle (left and right), supraspinatus insertion into greater tuberosity of humerus (left and right), greater trochanter (left and right), quadriceps insertion into superior border of patella (left and right), patellar ligament insertion into inferior pole of patella or tibial tubercle (left and right), Achilles tendon insertion into calcaneum (left and right), plantar fascia insertion into calcaneum (left and right). A higher count represents greater enthesitis burden.

Details of the scoring algorithm are described in [Appendix A](#).

Static Physician Global Assessment of Psoriasis (sPGA)

The static Physician Global Assessment of psoriasis (sPGA) evaluates the physician's global assessment of the subject's psoriasis based on severity of induration, scaling, and erythema. The sPGA is assessed on a scale of 0 (clear) to 5 (severe).

Swollen Joint Count

A score that assesses the presence or absence of swelling in 66 joints. Details of the scoring algorithm are described in [Appendix A](#).

Tender Joint Count

A score that assesses the presence or absence of tenderness in 68 joints. Details of the scoring algorithm are described in [Appendix A](#).

Treatment Emergent AE

A treatment emergent AE is defined as an event that occurs on or after the initiation of the IP and prior to the EOS date (ie, 30 days after last dose of IP). It is determined by the pre-treatment flag (ie, AE.AEPRETRT NE 'Y') on the Events CRF with a start date up to 30 days after the end of investigational product or the End of Study date, whichever is earlier.

Van der Heijde Modified Total Sharp Score (mTSS)

A method for assessing erosions and joint space narrowing of the hands and feet based on the Sharp-van der Heijde method in rheumatoid arthritis. The method is adapted for evaluation of PsA by including the distal interphalangeal joints of the hand and scoring not only for erosions and joint space narrowing but also for subluxation, ankylosis, gross osteolysis, and pencil in cup phenomena. The maximum possible total score is 528.

A higher score represents worse destruction. Details of the scoring algorithm are described in [Appendix A](#).

Very Low Disease Activity (VLDA)

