10.6.1 Adverse Events

The Medical Dictionary for Regulatory Activities (MedDRA) version 18.0 or later will be used to code all adverse events (AE) to a system organ class and a preferred term. All adverse event tables will be summarized by treatment group for the double-blind treatment period and the rescue therapy period. The subject incidence of AEs will be

summarized for all treatment-emergent AEs, serious AEs, AEs leading to withdrawal of investigational product, and fatal AEs.

Subject incidence of all treatment-emergent AEs, serious AEs, AEs leading to withdrawal of investigational product, and fatal AEs will be tabulated by system organ class and preferred term in descending order of frequency.

Summaries of treatment-emergent and serious AEs occurring in at least 1% of the subjects by preferred term in any treatment arm will be provided in descending order of frequency.

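### SAP 6.6 closes the treatment-emergent window in two different ways, and for a study withdrawer the derivation rule can exclude a collected SAE that falls within 30 days of last dose

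*SAP*

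**What the plan says.** SAP 6.6 defines a treatment-emergent AE in two sentences. The first requires onset on or after the start of IP and "prior to the EOS date (ie, 30 days after last dose of IP". The second states how the status is determined: a CRF flag that the event is not pre-treatment, "with a start date up to 30 days after the end of investigational product or the End of Study date, whichever is earlier".

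SAP 6.3 defines the End of Study date as the safety follow-up call for subjects who complete the study, "or Early Termination (ET) visit (for subjects who withdraw from the study prematurely". It separately defines the Last Dose Date: "The date of the last dose of IP".

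SAP 6.4 runs the double-blind period from first dose "through the first dose of rescue treatment, or end of study if they are never rescued", and the rescue period from the "first dose of open-label rescue therapy at or after week 24 through end of study". SAP 10.6.1 then says: "All adverse event tables will be summarized by treatment group for the double-blind treatment period and the rescue therapy period". Subject incidence is to be "summarized for all treatment-emergent AEs, serious AEs, AEs leading to withdrawal of investigational product, and fatal AEs".

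On collection, Protocol 9.2.2 requires SAEs to be reported through 30 days after the last day of the dosing interval. Protocol 7.2.7 plans a call for SAEs about 30 days (window +7 days) after last dose and does not limit it to completers. Protocol 9.2.1 collects non-serious AEs only through the end of the treatment period.

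**The concern.** The first sentence treats the EOS date and 30 days after last dose as the same day. The second takes the earlier of the two, which has a purpose only if they can differ. Under SAP 6.3 they do differ for a subject who leaves the study early, because that subject's End of Study date is the ET visit. An SAE after that visit but within 30 days of last dose would then be collected and yet classed as not treatment-emergent.

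A withdrawer could therefore have a shorter window than a completer, and the count would depend on which sentence is programmed. Only SAEs, including fatal ones, are at stake in this tail, because non-serious AEs are no longer collected. SAEs are few and are read one by one.

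**Working it through.** The documents give no stated figure to reproduce here. The check is date logic followed by an illustration of scale.

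**Where the window closes.** Count days from last dose and let *g* be the day of the ET visit. The documents give no interval from last dose to that visit, so the values of *g* are assumptions.

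- 30-day gloss in SAP 6.6: day 30.
- Derivation sentence with SAP 6.3: min(30, *g*).
- Days cut: 30 − min(30, *g*).

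| ET visit (*g*) | Gloss | Derivation sentence | Days cut |
|---|---|---|---|
| 0 | 30 | 0 | 30 |
| 7 | 30 | 7 | 23 |
| 14 | 30 | 14 | 16 |
| 21 | 30 | 21 | 9 |
| 30 or later | 30 | 30 | 0 |

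**Example.** Last dose is on day 100, the ET visit on day 107 and an SAE on day 115. The gloss closes at 100 + 30 = day 130, so the SAE is treatment-emergent. The derivation sentence closes at min(130, 107) = day 107, so it is not.

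**Completers.** With the call on day 30 to 37 after last dose (Protocol 7.2.7), min(30, 30 to 37) = day 30, the same as the gloss. What remains is one day: the first sentence excludes the limit day and the second includes it.

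**Who is exposed.** The subject must leave the study, have an ET visit within 30 days of last dose, and have SAE data afterwards. Protocol 8.3.2 gives four reasons for removal from the study.

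- Death without an ET visit: no truncating date.
- Loss to follow-up: later SAE data are unlikely.
- Withdrawal of consent: Protocol 8.1 says later data may not be included, except that a possibly related SAE is still collected.
- Sponsor decision: later SAEs can be collected under Protocol 7.2.7 and 9.2.2.

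The last group, and possibly related SAEs in the third, make up most of the exposure. A subject who stops IP but stays in the study has a later End of Study date and is not truncated.

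**Scale.** Person-years cut = n × (30 − *g*)/365.25. The 10% dropout in Protocol 10.2 is a sample-size allowance and not a bound, so 5 to 20% of 840 is shown. SAE rates of 0.05 to 0.20 per person-year are assumed. Every dropout is counted as having an ET visit and full later SAE data, which is well above what Protocol 8.1 and 8.3.2 support.

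| Dropout | n | *g* | Person-years cut | Expected SAEs, all arms |
|---|---|---|---|---|
| 5% | 42 | 7 | 42 × 23/365.25 = 2.64 | 0.13 to 0.53 |
| 10% | 84 | 7 | 84 × 23/365.25 = 5.29 | 0.26 to 1.06 |
| 10% | 84 | 21 | 84 × 9/365.25 = 2.07 | 0.10 to 0.41 |
| 20% | 168 | 7 | 168 × 23/365.25 = 10.58 | 0.53 to 2.12 |

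Planned observation is 840 × (336 + 30)/365.25 = 841.7 person-years. The 10%, 7-day case is 5.29/841.7 = 0.63% of that.

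**Collection against analysis.** Protocol 9.2.2 counts 30 days from the last day of the dosing interval, not from last dose. The documents do not define that day. With weekly dosing (Protocol 6.2.1.1 and 6.2.2.1) it plausibly falls several days after the last dose, so a window ending exactly 30 days after last dose could still miss collected SAEs, in completers too.

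**The case against.** The best defence is that the two sentences do different jobs: the first describes and the second derives, so a programmer would follow the second and there is one rule in practice. Much of that stands. Other readings can be built, such as substituting the SAP 6.3 date into the first sentence over its own gloss, or reading the cap as 30 days after the earlier date, but they are strained. A reader might infer several equally plausible windows; the text does not support that. The defence does not remove the conflict, however, because the operative rule is the one that truncates. If the gloss is meant to govern instead, the End of Study alternative serves no purpose.

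A reader might also infer that completers are truncated. For a call within its stated window they are not.

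A third tempting inference is that SAEs or deaths disappear from the safety report. SAP 10.6.1 and Protocol 10.5.4 list serious and fatal events beside treatment-emergent ones without saying they are a subset, so those tables may still show the event. It would fall outside both table periods only if the end of study in SAP 6.4 means the SAP 6.3 date, which is not stated. The protocol glossary ties a subject's EOS to the last protocol-specified procedure, which could be the follow-up call even after early termination.

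Finally, the events still reach the sponsor, and no formal testing is done on safety (SAP 10.1).

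**Conclusion.** The inconsistency is real and minor. As written, SAP 6.6 with SAP 6.3 can class an SAE as not treatment-emergent when it follows an ET visit but lies within 30 days of last dose. This rests on the derivation sentence being implemented as a cap at the earlier date, and on an ET visit less than 30 days after last dose with SAE data afterwards.

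The likely size is at most a very few SAEs in the whole trial. The largest case tabulated is about 2, and it counts every dropout at a 20% rate as exposed. Because exposure is mainly sponsor-decision exits and possibly related SAEs after withdrawal of consent, the true figure should be lower. The ET interval and SAE rates are assumptions. A reader might infer a bias between arms, but nothing in the documents shows that the cut would fall unequally.

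**What to change.** 1. In SAP 6.6, delete the clause that offers the End of Study date as an alternative limit, and replace the EOS-date condition in the first sentence with one window for every subject: first dose of IP through 30 days after last dose, using the Last Dose Date already in SAP 6.3. Make the final day inclusive in both sentences.
2. Reconcile that end point with the SAE collection window in Protocol 9.2.2, which counts from the last day of the dosing interval, so that collected SAEs are not cut.
3. For AE tables only, assign an event in this tail to the subject's last treatment period: double-blind if never rescued, rescue if rescued.

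Leave the End of Study date and the periods used for efficacy unchanged. The cost is a wording change, one date derivation and one period rule, with no new data collection. The downside is that the treatment-emergent count may be slightly higher.

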7.1 Full Analysis Set

The full analysis set will include all randomized subjects. Subjects will be analyzed according to their randomized treatment group. Demographics, baseline disease characteristics, and non-psoriasis efficacy analyses will be based on the full analysis set.

7.2 Psoriasis Efficacy Analysis Set

The psoriasis efficacy analysis set will include all randomized subjects with baseline BSA $\geq 3\%$. Subjects will be analyzed according to their randomized treatment group. Analyses of psoriasis efficacy endpoints (eg, sPGA, BSA) will be based on the psoriasis efficacy analysis set.

7.3 Safety Analysis Set

The safety analysis set will consist of all randomized subjects who receive at least one dose of investigational product. Subjects will be analyzed according to the actual treatment received as defined in [Section 6.1](#). Analyses of safety endpoints will be based on the safety analysis set.

7.4 Adequate Methotrexate Analysis Set

The adequate methotrexate analysis set will consist of all randomized subjects who receive weekly dose of at least 15 mg of methotrexate for at least 15 weeks during the course of week 4 (inclusive) to week 24 (inclusive) on etanercept plus methotrexate arm or methotrexate mono arm, and all subjects randomized to etanercept mono arm.

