### **6.2.2 Non-Amgen Investigational Product: Methotrexate**

Non-Amgen investigational product methotrexate will also be used in this study. Methotrexate will be distributed using Amgen clinical trial drug distribution procedures. Methotrexate will be supplied as 2.5 mg methotrexate capsules or as matching placebo capsules. For those subjects receiving rescue therapy, methotrexate will be dispensed as 2.5 mg tablets.

Additional details regarding the product(s) are provided in the IPIM.

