#### **6.2.2.1 Dosage, Administration, and Schedule**

Methotrexate dosing will be initiated at 10 mg weekly and will be titrated up to a final dose of 20 mg weekly over a 4-week period. The treatment period for this study is 48 weeks. Methotrexate will be provided as 2.5 mg capsules, or as placebo capsules, and will be taken once weekly by oral administration. Capsules should be swallowed whole. Subjects will receive 1 dose of methotrexate or placebo per week (scheduled approximately 7 days apart) for 48 weeks. Throughout the entire trial, administration of methotrexate or matching placebo should occur on the scheduled dose day; however, if unavoidable, it may be given earlier or later as long as the dose is not within 4 days of the next scheduled dose. If the dosing window is missed, that dose should be skipped and the next dose should be resumed at the scheduled time. The reason for the missed

dose must be reported on the eCRF. Double or extra doses should not be taken. The start date, quantity administered, and bottle/package number of methotrexate is to be recorded on the subject's diary and entered into the eCRF.

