#### **6.2.2.2 Dosage Adjustments, Delays, Rules for Withholding or Restarting, Permanent Discontinuation**

Methotrexate (or placebo for methotrexate) will be initiated at a dosage of 10 mg weekly at week 0 (day 1). The dose will be increased by 2.5 mg weekly up to 20 mg over a 4 week period. In cases of typical methotrexate toxicities (eg, increased aspartate transaminase or alanine transaminase, or gastrointestinal adverse effects, severe stomatitis), the methotrexate dose may be reduced up to 10 mg weekly. The reason for dose change of methotrexate is to be recorded on each subject's eCRF.

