### **10.5.2 Primary and Key Secondary Efficacy Endpoints**

The primary analysis for the primary endpoint and key secondary endpoints, ACR 20 response and MDA response at week 24, will be performed using the full analysis set. Treatment effect will be tested using the stratified CMH test with baseline BMI and prior non-biologic DMARD use as the stratification factors.

[figure not shown]
To control the family-wise 2-sided type one error rate at 0.05 for the multiple comparisons of the etanercept plus methotrexate therapy and etanercept monotherapy

groups with methotrexate monotherapy across the primary and key secondary endpoints, the hypotheses will be tested using a Bonferroni-based gatekeeping chain procedure (Burman et al, 2009 and Millen et al, 2011) as shown in Figure 1. This procedure will split alpha of 0.05 equally to test in parallel the primary and key secondary endpoints (ACR 20, MDA) for etanercept plus methotrexate therapy vs. methotrexate monotherapy and etanercept monotherapy vs. methotrexate monotherapy sequentially within each parallel path. If one of the parallel paths rejects both hypotheses sequentially, and the other parallel path has at least one hypothesis not rejected, then unspent alpha of 0.025 from the successful path will be propagated to the hypotheses in the other path to re-test them sequentially at a level of 0.05. For example, suppose the nominal p-values for hypotheses A1, B1, A2, and B2 (Figure 1) are 0.01, 0.02, 0.03, and 0.055, respectively. In the first round of testing, hypotheses A1 and B1 are rejected, whereas hypotheses A2 and B2 are not rejected. However, since both hypotheses A1 and B1 are rejected, the procedure gives a second chance to re-test hypotheses A2 and B2 (according to the left arm of the figure) at a lower threshold of 0.05 rather than the original threshold of 0.025. Note that in this example A2 is rejected and hypothesis B2 is not rejected.

Figure 1. Bonferroni-based Gatekeeping Chain Procedure

ETN: Etanercept; MTX: Methotrexate

For the primary analysis of the primary and key secondary endpoints, missing data will be imputed as nonresponder. Sensitivity analyses using observed data and using last observation carried forward imputation will also be performed.

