9.3.2 Missing Post-baseline Evaluation

Subjects with missing post-baseline efficacy data will be imputed as non-responder, ie, non-responder imputation (NRI) for the primary analysis of primary and key secondary efficacy endpoints (ACR 20 and MDA). Data will also be analyzed using multiple imputation (MI) as sensitivity analyses for primary and key secondary endpoints (ACR20 and MDA).

For analyses of other efficacy endpoints after week 24, data from subjects who remain in the double-blind period will be analyzed as observed with no imputation for missing data. Data from subjects who enter open-label rescue therapy will be imputed using last observation carried forward (LOCF).

For non-radiograph exploratory endpoints, data will be analyzed as observed without imputation for missing data.

For radiographic exploratory endpoints, data will be analyzed as observed with no imputation for missing data or for subjects who enter rescue treatment. In addition, data will be analyzed using LOCF imputation for missing radiographs and for subjects who enter rescue treatment as sensitivity analysis.

Baseline data will not be carried forward to any missing post-baseline value unless otherwise specified.

Missing post-baseline safety data will not be imputed.

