9.4 Detection of Bias

The study has been designed to minimize potential bias by selecting subjects, allocating treatment groups, assessing endpoints, and handling withdrawals without knowledge of the treatment. Other factors that may introduce bias include:

- Important protocol deviations likely to impact the analysis or interpretation of results
- Blind breaking before database lock and formal unblinding
- IP dosing non-compliance
- Reasons for early withdrawal from treatment or from study

The incidence of these factors will be assessed. Important protocol deviations likely to impact the analysis and interpretation of results will be listed and/or tabulated in the Clinical Study Report (CSR). If a significant number of major protocol deviations are observed, an additional sensitivity analysis may be performed on the efficacy data excluding subjects with major protocol deviations.

Any breaking of the blind for individual subjects prior to formal unblinding of the study will be documented in the CSR, including the timing and reason for unblinding. The impact of such unblinding on the results will be assessed.

Tabulations of important protocol deviations (IPDs) related to IP dosing non-compliance by treatment group will be provided. A sensitivity analysis including subjects who tolerated at least 15 mg weekly of methotrexate (or placebo for methotrexate) after the initial 4-week titration through week 24 will be performed to assess the potential bias of methotrexate intolerance, as previously described in [Section 7.4](#).

Reasons for early withdrawals from treatment and from study will be summarized. If a significant pattern is observed, additional sensitivity analyses may be performed on efficacy data adjusting for reasons for early withdrawal.

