In addition, the primary and key secondary endpoints will be analyzed using multiple imputation (MI) as a sensitivity analysis. Another sensitivity analysis for primary and key secondary endpoints will also be performed using Adequate Methotrexate Analysis Set. Sensitivity analyses of primary and key secondary endpoints are descriptively without adjusting for multiplicity.

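### SAP 7.4 filters the two methotrexate arms on exposure but keeps every etanercept-mono subject; SAP 9.4 says otherwise, and the one-sided set can bias a sensitivity analysis against etanercept mono

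*SAP*

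**What the plan says.** SAP 7.4 sets a minimum of 15 weeks at 15 mg or more of methotrexate, counted from week 4 to week 24 inclusive, for subjects "on etanercept plus methotrexate arm or methotrexate mono arm, and all subjects randomized to etanercept mono arm". No exposure condition applies to etanercept mono.

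SAP 9.4 describes an analysis of "subjects who tolerated at least 15 mg weekly of methotrexate (or placebo for methotrexate) after the initial 4-week titration through week 24". It says the purpose is to assess possible bias from methotrexate intolerance, and it refers back to Section 7.4 for the definition.

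SAP 10.5 and 10.5.1 name the set as the basis of a sensitivity analysis of ACR 20 and MDA, next to multiple imputation, and do not restate who is in it. On its status, 10.5.1 says: "Sensitivity analyses of primary and key secondary endpoints are descriptively without adjusting for multiplicity". Protocol 10.5.2 names two further sensitivity analyses: "Sensitivity analyses using observed data and using last observation carried forward imputation will also be performed".

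SAP 9.3.2 and 10.5.1 specify non-responder imputation (NRI) for the primary analysis of ACR 20 and MDA. No rule for missing responses is given for the Adequate Methotrexate Analysis Set.

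**The concern.** Only etanercept mono takes placebo for methotrexate, so the reference to placebo in 9.4 can only mean that this arm is filtered too. Section 7.4 says it is not. Two programmers working from the two sections could build different sets and report different etanercept-mono rates.

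The one-sided rule in 7.4 also has a direction. It removes most early stoppers, and subjects held below 15 mg, from methotrexate mono, while the corresponding subjects stay in etanercept mono. If those removed respond below their arm's average, the methotrexate rate rises and the difference shrinks with no change in drug effect. An analysis meant to gauge bias from intolerance could then add a bias of its own, and a smaller etanercept-mono effect could come from the set definition alone. The risk is a falsely discouraging or uninterpretable supporting result.

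**Working it through.** **The two definitions side by side**

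| | SAP 7.4 | SAP 9.4 |
|---|---|---|
| Combination arm | filtered on methotrexate | filtered on methotrexate |
| Methotrexate mono | filtered on methotrexate | filtered on methotrexate |
| Etanercept mono | everyone kept | filtered on placebo for methotrexate |
| Duration | at least 15 weeks within weeks 4–24 | after titration through week 24, no 15-week minimum |

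Weeks 4 to 24 inclusive hold 24 − 4 + 1 = 21 weekly doses, so 7.4 asks for 15 of 21 (71%).

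**Inputs from SAP 3.2.** Planned ACR 20 is 60% (etanercept mono) and 44% (methotrexate mono), a 16.0-point difference. Planned MDA is 30% and 15%, a 15.0-point difference. Two-sided alpha is 0.025, power 90%, dropout 10%, and about 280 subjects per arm.

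**The plan's own figure.** A two-proportion test of 44% against 60% at these settings needs 253 per arm with continuity correction, and 253/0.9 rounds up to 282, in line with 280. Without the correction it needs 240 per arm, or 267 after dropout. The planned rates are therefore a sound base for the check.

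**Formula.** Let p be the arm rate, e the share excluded and r the response among those excluded. The rate among those kept is (p − e·r)/(1 − e). The documents give neither e nor r, so both are assumptions, shown as ranges.

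**Reading A: the planned rates are full-set NRI rates; methotrexate mono is filtered and etanercept mono is not.** With e = 10%, the methotrexate ACR 20 rate becomes
- 44/0.9 = 48.9 if r = 0
- (44 − 2.2)/0.9 = 46.4 if r = 22 (half the arm rate)
- 44.0 if r = 44

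Differences in percentage points, etanercept mono minus methotrexate mono:

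| Share excluded | ACR 20, r = 0 | ACR 20, half rate | MDA, r = 0 | MDA, half rate |
|---|---|---|---|---|
| 5% | 13.7 | 14.8 | 14.2 | 14.6 |
| 10% | 11.1 | 13.6 | 13.3 | 14.2 |
| 20% | 5.0 | 10.5 | 11.3 | 13.1 |

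When r equals the arm rate there is no shift (16.0 and 15.0). When r is above it the shift reverses: with e = 10% and r = 60, (44 − 6)/0.9 = 42.2 and the difference is 17.8.

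If both arms truly had 44%, the one-sided filter with r = 0 would show 44 − 48.9 = −4.9 points at 10% excluded and 44 − 55 = −11.0 at 20%. A filter with equal exclusion and equal r in both arms would show 0.

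**Reading B: the planned rates are completer rates, with 10% dropout scored as non-response.**
- Full set: 0.9 × 60 − 0.9 × 44 = 54.0 − 39.6 = 14.4.
- All methotrexate dropouts removed: 54.0 − 44.0 = 10.0.
- Some dropouts kept: 15 doses from week 4 are complete by week 18, so with dropout uniform over 24 weeks (assumed) 6/24 = 25% of dropouts stay in. Then 54.0 − 39.6/0.925 = 11.2.
- MDA: 27.0 − 13.5 = 13.5 in the full set; 27.0 − 15.0 = 12.0 with all dropouts removed; 27.0 − 13.5/0.925 = 12.4 with a quarter kept.

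**Reading C: observed data only.** Dropout by itself causes no shift, because dropouts leave both arms. If 5% stay on study below 15 mg and respond at half the rate, ACR 20 is 60 − 45.2 = 14.8 and MDA is 30 − 15.4 = 14.6.

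**Same rule in both arms, reading A, ACR 20.**
- 10% excluded in each arm: 66.7 − 48.9 = 17.8 (r = 0), or 63.3 − 46.4 = 16.9 (half rate).
- 5% excluded on placebo and 10% on methotrexate: 63.2 − 48.9 = 14.3, or 61.6 − 46.4 = 15.1 (computed from unrounded values).

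**The case against.** Section 9.4 points back to 7.4, and 10.5 and 10.5.1 use only the name that 7.4 defines, so a programmer would probably build the 7.4 set. That is likely in practice, but it does not remove the conflict: 9.4 claims to describe the same set and includes placebo.

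The strongest argument is that the one-sided set can serve as a stress test. Stopping a placebo capsule is not methotrexate intolerance, and keeping all of etanercept mono asks whether it still does better than adequately dosed methotrexate. A surviving effect would then be reassuring. The SAP does not give this rationale, however, and the wording of 9.4 runs against it.

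Several limits stand:
- The size of the bias rests on assumptions. The largest shifts need every excluded subject to be a non-responder. Protocol 6.2.2.2 says "the methotrexate dose may be reduced up to 10 mg weekly", so an excluded subject may still be on treatment and responding. The rule also tolerates about 6 of 21 missed or low-dose weeks.
- A colleague could reasonably read NRI as carrying over to this set, since only the population is said to change. On its own, the missing sentence would be a matter of detail.
- The combination and methotrexate mono arms face the same filter, so that comparison lacks this asymmetry.
- A symmetric rule is not unbiased either, as the last figures in the working show. Subjects who tolerate placebo need not resemble those who tolerate methotrexate.

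**Conclusion.** The concern holds. SAP 7.4 and 9.4 contradict each other on whether etanercept mono is filtered, and on duration. As written, the 7.4 rule biases etanercept mono against methotrexate mono downwards whenever the excluded methotrexate subjects respond below those kept. With 5% to 20% excluded under reading A, the ACR 20 difference falls from 16.0 to between 13.7 and 5.0 (all non-responders) or between 14.8 and 10.5 (half rate); MDA moves much less. The text conflict is certain. The size of the bias is conditional on the excluded share, its response and the missing-data rule, and it is zero if those excluded respond at the arm rate.

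The consequence is confined to a descriptive analysis; the gatekept tests on the full analysis set and their type I error are untouched. It should still be corrected, because it is one of only two sensitivity analyses that SAP 10.5.1 specifies for ACR 20 and MDA. Choosing between the two definitions after unblinding would be open to challenge.

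**What to change.** Follow 9.4 and apply one capsule-exposure rule to all three arms. Protocol 6.2.2 makes this feasible: "Methotrexate will be supplied as 2.5 mg methotrexate capsules or as matching placebo capsules". The 15 mg threshold is 15/2.5 = 6 capsules. Possible text for 7.4:

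> *Randomized subjects, in any arm, who took six or more 2.5 mg capsules (active or matching placebo) weekly for 15 or more weeks from week 4 to week 24 inclusive.*

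Use the same duration in 9.4. Add a sentence on missing responses in this set, for example NRI as in the primary analysis. State that the set still selects on exposure after randomization and is descriptive only. Merely aligning 9.4 to 7.4 would end the contradiction but leave the asymmetry.

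The cost is about one sentence each in 7.4 and 9.4 and one on missing data. No new data should be needed: Protocol 6.2.2.1 says "quantity administered, and bottle/package number of methotrexate is to be recorded" in the diary and eCRF. That sentence names methotrexate only, but under blinding it must in practice cover the placebo capsules as well. The etanercept-mono set becomes slightly smaller.
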